
and prognostic values. A biomarker is a parameter that is objectively measured and evaluated as an indicator of normal biological, pathogenic processes or responses to therapeutic intervention. The imbalance between bacterial load and host response at the soft tissueimplant interface triggers an inflammatory process. Cytokines such as tumor necrosis factor alpha, Interleukin-1-beta, and Interleukin-6 are produced by dendritic cells, connective tissue fibroblasts, macrophages, and neutrophils, as well as a number of enzymes, such as matrix metalloproteinases, by neutrophils, fibroblasts, and osteoclasts, which promote the synthesis of connective tissue collagen, and causes deterioration of alveolar bone. Such cytokines and enzymes can be detected in peri-implant groove fluid by various tests and allow objective evaluation in determining prognosis (11). Nowadays, periodontal and transgingival probing measurement techniques are frequently used to determine gingival thickness. In our study, peri-implant mucosa phenotype will be measured with a newly developed probe (Hu-Friedy Colorvue Biotip Probe®) with a colored tip that will be placed in the gingival sulcus, and the relationship between peri-implant disease and peri-implant phenotype will be investigated. Additionally, since the method to be applied is different, whether it is a reliable method will be compared with the literature and the conventional method (transgingival probing). In our study, connective tissue graft, one of the soft tissue augmentation methods, will be applied to the areas where thin biotypes are detected as a result of our analysis methods. Recent studies (12) have emphasized that soft tissue augmentation procedures applied in areas with periimplant disease can provide significant reductions in bleeding on probing and gingival index values, and in addition, there may be an increase in marginal bone levels. In the light of all this information, the aim of our study is to investigate the effect of peri-implant soft tissue phenotype on the degree of peri-implant disease and its contribution to the results of nonsurgical mechanical treatment, accompanied by clinical and biochemical parameters.

Study Protocol, Methods and Procedures to be Applied: Patient Selection and Study Protocol

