Peri-implant crevice fluid (PIOS) samples will be collected from all individuals before proceeding with mechanical treatment of diseased implant sites. The areas will be isolated from saliva with cotton pellets, dried with light air, and paper strips (PerioPaper®) will be kept in the trough for 30 seconds (13). Paper strips obtained from each implant will be placed in Eppendorf tubes containing isotonic Ph:7.4 phosphate buffer solution and stored at -40 ° C until analyzed in the laboratory department of our clinic. Routine periodontal parameters such as plaque index (PI) (14), gingival index (GI) (14), bleeding on probing and probing pocket depth scores of the patients whose PIOS samples are collected will be recorded with a Williams-type plastic probe. Following these procedures, the patients' peri-implant phenotype will be evaluated. In the evaluation, the traditional transgingival probing technique and a newly developed technique will be used simultaneously and their correlations with each other

will be examined. A digital caliper with a sensitivity of 0.01 mm will be used to measure transgingival probing values to determine peri-implant mucosa thickness. Measurements will be made from two points: apical of the free gingival sulcus and coronal of the mucogingival junction. After the peri-implant mucosa thickness measurement points are determined with a marker pen, Xylocaine® spray (Vemcaine 10%, lidocaine) or, if necessary, local anesthetic (Maxicaine, lidocaine hydrochloride) will be applied to prevent the patient from feeling pain. Measurements will be made from the marked points in a direction perpendicular to the peri-implant mucosa, using a 10-gauge endodontic spreader (G-Star Medical Co., Ltd., Guangdong, China) with a silicone stopper until its contact with the alveolar bone is felt. Since excessive force will cause the spreader to exceed the soft tissue and advance in the alveolar bone, care should be taken to apply only light forces that can be limited to the soft tissue. After all measurements are repeated twice by the same researcher at 10-minute intervals, the amount of peri-implant mucosa thickness in each region will be determined by taking the average of the two measurements.

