If the millimetric values obtained as a result of measurements are less than 1 mm, thin phenotype; If it is more than 1 mm, it will be classified as thick phenotype (15). The second gingival phenotype evaluation in individuals with peri-implant disease will be performed with the Hu-Friedy Colorvue Biotip Probe[®], a newly developed probe with a colored tip that will be placed in the peri-implant pocket. The white probe will first be placed in the peri-implant pocket with a pressure of less than 25 N. If the color of the probe reflects from the gingival tissue, the phenotype will be recorded as thin. If the white color is not visible, the green probe will be placed in the pocket in the same way and if the color is reflected, the phenotype will be classified as medium thickness. If the Green tip is not visible through the gingival tissue, the Blue probe will be used and if the only color seen is Blue, the phenotype will be classified as thick. If blue is not visible, the peri-implant mucosa tissue will be recorded as too thick. Then, traditional mechanical debridement with titanium curettes will be applied to the areas with peri-implant disease without losing the effect of anesthesia. The area will be irrigated with physiological saline from time to time. Following the procedure, patients will be called for control at the 1st, 3rd and 6th months. Oral hygiene instructions will be repeated when necessary. At the 6th month, all clinical parameters examined will be measured again and PIOS samples will be collected again. 6th month following the operation; PIOS samples will be collected again from all operated patients and the clinical parameters examined will be recorded.

Immunohistochemical Analysis

After the target number of patients is reached, the PICF samples collected will be sent to the laboratory for analysis using ELISA (Enzyme-linked immunosorbent assay) kits.

Statistical analysis

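### The colour-probe reading is described as coming after marking, anaesthesia and puncture, with no masking of the caliper result, although the plan also calls the two techniques simultaneous

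*Combined protocol and SAP*

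**What the plan says.** The last paragraph of the scientific background (combined protocol and SAP) makes the comparison of techniques an additional aim. For the new probe, "whether it is a reliable method will be compared with the literature and the conventional method (transgingival probing".

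The section Patient Data Records, Peri-implant Disease Treatment then makes two statements about timing that do not fit together. In general terms, "the traditional transgingival probing technique and a newly developed technique will be used simultaneously and their correlations with each other" are to be examined. In detail, the steps follow one another:

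- The crevice fluid sample is taken and the routine indices, including pocket depth, are recorded.
- The site is marked and numbed: "After the peri-implant mucosa thickness measurement points are determined with a marker pen, Xylocaine® spray (Vemcaine 10%, lidocaine) or, if necessary, local anesthetic" is applied.
- Thickness is measured with a spreader: "Measurements will be made from two points: apical of the free gingival sulcus and coronal of the mucogingival junction". The spreader is advanced "with a silicone stopper until its contact with the alveolar bone is felt".
- The thickness of each region is the average of two measurements: "After all measurements are repeated twice by the same researcher at 10-minute intervals". A 1 mm rule then gives thin or thick.
- The colour probe follows: "The second gingival phenotype evaluation in individuals with peri-implant disease will be performed with the Hu-Friedy Colorvue Biotip Probe". The class (thin, medium, thick or too thick) depends on which coloured tip can be seen through the tissue.
- Debridement comes next, while the anaesthesia still acts.

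The Statistical analysis section plans Pearson or Spearman correlations. The plan does not say who reads the colour probe, whether that person is masked to the caliper value, or whether the order is varied or the tissue is left to recover.

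**The concern.** In a comparison of two techniques, the reading under evaluation should not be altered or informed by the reference reading. Taken in the written order, the colour reading is exposed to both.

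The first route is physical. The result is whether a coloured tip shows through the mucosa, and ink, bleeding, blanching or local anaesthetic fluid at or near the site could change that. The second route is expectation. Show-through is a visual judgement, and nothing in the plan keeps the caliper value from the person who makes it.

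What is at stake is the interpretation of the reliability comparison. Close agreement might partly reflect knowledge of the caliper value, and poor agreement might partly reflect disturbed tissue. Replacing the planned correlation with an agreement statistic would not help, because it would be computed from the same readings.

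**Working it through.** The plan states no agreement, power or sample-size figure for this comparison, so there is nothing of its own to reproduce. The check is a tracing of the order, followed by an illustration on assumed inputs.

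**Order.** The marker pen and anaesthetic precede the spreader. The number of punctures before the colour probe is 2 points × 2 measurements = 4 per region, with 10 minutes between the two rounds. The colour probe is called the second evaluation, and debridement follows under the same anaesthesia. Marking, anaesthesia, puncture, colour reading and debridement therefore belong to one sitting, and the colour reading is made under active anaesthesia. Literal simultaneity is not compatible with these steps.

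**Illustration of the expectation route.** Assume two classes with equal margins, and that a share f of colour readings simply follows the caliper class. Chance agreement is 0.5, so κ = 2p − 1. Observed agreement is p_obs = f + (1 − f)p, hence κ_obs = f + (1 − f)κ_true. For example, 0.30 + 0.70 × 0.50 = 0.65.

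| κ_true | f = 10% | f = 20% | f = 30% |
|---|---|---|---|
| 0.30 | 0.37 | 0.44 | 0.51 |
| 0.50 | 0.55 | 0.60 | 0.65 |
| 0.70 | 0.73 | 0.76 | 0.79 |

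**Illustration on the planned type of statistic.** The probe has four classes and the plan is a correlation, so a simulation of 200,000 sites is closer to the planned data. All its inputs are assumed: thickness mean 1.1 mm and SD 0.4 mm; caliper error SD 0.15 mm; probe error SD 0.3 or 0.5 mm; colour-class limits at 0.8, 1.1 and 1.4 mm.

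- With 30% of readings anchored to the caliper value, Spearman's rho rises from 0.70 to 0.77 (probe error 0.3 mm) or from 0.53 to 0.65 (probe error 0.5 mm).
- With a uniform 0.2 mm apparent thickening that affects the probe only, rho goes from 0.70 to 0.69 or from 0.53 to 0.52. Thin/thick kappa goes from 0.53 to 0.48 or from 0.39 to 0.38.

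On these assumptions, expectation inflates the correlation, while a uniform tissue shift slightly lowers agreement and is almost invisible to a correlation. None of the shares or shifts comes from the documents.

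**The case against.** The strongest reply is that neither route is established.

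- **Knowledge of the caliper value.** A reader might infer that the colour-probe examiner already knows the caliper value and its class. The documents do not say so. The mention of the same researcher covers only the repeated transgingival measurements, the colour-probe examiner is not named, and the time at which the average is worked out is not given. What stands is narrower: no masking or separate examiner is stated.
- **Order.** The word second might only number the methods, and the text does say simultaneous. This has some force, but the carry-on to debridement under the same anaesthesia makes a sequence the natural reading. The conflict needs resolving in any case.
- **Physical overlap.** The punctures are at two marked points on the mucosa, whereas the colour probe sits in the pocket. Anaesthetic other than the spray is used only if necessary. Carry-over is therefore plausible but not shown. Pocket probing also comes before both techniques, so no order guarantees a site free of bleeding.
- **Size.** The kappa table reduces four colour classes to two and rests on assumed shares. It illustrates the mechanism and does not estimate the bias.
- **Importance.** The comparison is an additional aim. The main aim concerns phenotype, disease and treatment response, and no effect on it is shown here. This limits the weight of the point.

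**Conclusion.** The point stands as a risk of bias in a secondary comparison, together with an inconsistency over timing. As described, the colour reading comes second, after marking, anaesthesia and repeated puncture, and no masking is stated.

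A reader might go further and conclude that the comparison is certainly contaminated, or that no agreement result could be attributed to the probe. The documents do not support that: they give no data on either route, and the two may act in opposite directions. The size and net direction are therefore undetermined, and the figures above show only what assumed shares would do. The conclusion rests on reading the steps as a sequence in one sitting. It does not depend on who the examiner is, because the physical route exists whoever reads the probe. It is worth acting on because the remedy is nearly free.

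**What to change.** Reconcile the statement that the techniques are used simultaneously with the sequence described. State that the colour-probe class is taken and written down after the fluid sample and the indices, but before the marker, the anaesthetic and the transgingival puncture. Use the same order at month 6 if phenotype is re-measured then; the plan says only that all clinical parameters examined are measured again. Record who makes each reading.

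This removes both routes of carry-over from the transgingival measurement onto the colour reading. A second examiner masked to the caliper value would deal with expectation alone and would leave the tissue change.

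The cost is a sentence or two in the protocol, with no added visit, procedure or change in sample size. There are two small downsides. The colour probe is used before anaesthesia, as the pocket-depth probe already is. The transgingival reading depends on felt bone contact, so it could still be slightly influenced by the recorded colour class, although it is a measurement in millimetres and so less open to suggestion than a visual class.

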COVER PAGE

Peri-implant Phenotype, Calprotectin and Mmp-8 Levels in Cases Diagnosed With Periimplant Disease

[name] DDS, PhD¹, [name] DDS, PhD²

¹Bilecik Şeyh Edebali University, Faculty Of Dentistry, Department of Periodontology, Bilecik, Turkey

²Van Yuzuncu Yıl University, Faculty of Dentistry, Department of Periodontology, VAN,

Turkey

Corresponding Author: [name]

Address: Bilecik Şeyh Edebali University, Faculty Of Dentistry, Department of

Periodontology, [name]

E-mail address: [contact] [contact] Office [contact]

[name]

Bilecik Şeyh Edebali University, Faculty Of Dentistry, Department of Periodontology, [name]

E-mail address: [contact] [contact] Office [contact]

[name]

Van Yuzuncu Yıl University, Faculty of Dentistry, Department of Periodontology, VAN,

Turkey

E-mail address: [contact] [contact]

STUDY PROTOCOL AND STATISTICAL ANALYSIS PLAN

Aim of Research: In this study, it was aimed to investigate the effect of peri-implant soft tissue phenotype on the degree of peri-implant disease and its contribution to the results of non-surgical mechanical treatment, accompanied by clinical and biochemical parameters. The research hypothesis is that better clinical outcomes may be achieved in individuals with thicker soft tissue phenotype.

Scientific Basis and Validity of Medical Research:

Over the last two decades, dental implants have been used to replace missing teeth; It has become a widely accepted and applied therapeutic method to support fixed and removable prostheses (1). A dental implant is generally defined as a root form made of titanium that is placed in place of a natural tooth (2).

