Bacterial pathogens (i.e., periodontal pathogens with a similar composition of the oral microbiota that cause chronic periodontitis) represent the primary etiological factor for periimplant diseases. Additionally, an imbalance of individual local inflammatory response and host-parasite interaction is also implicated for the onset of inflammatory peri-implant diseases. Various risk factors (such as poor oral hygiene, smoking, uncontrolled diabetes, genetic characteristics, alcohol consumption and implant surface) play a role in peri-implant tissue destruction. Insufficiency of keratinized mucosa has also been investigated as a possible risk factor for periimplant diseases (8). Phenotype refers to a dimension that may change over time depending on environmental factors and clinical intervention, and may be site-specific. Periodontal phenotype (3-dimensional image of the gingiva) is determined by gingival phenotype (gingival thickness, keratinized tissue width) and bone morphotype (buccal bone thickness) (9). Peri-implant phenotype can be defined as the dimensional, morphological and topographic features that characterize the clinical condition of the tissues surrounding and supporting osseointegrated implants. The peri-implant phenotype encompasses a soft tissue component, including the osseous component characterized by peri-implant keratinized tissue width, mucosal thickness and supracrestal tissue height, and peri-implant bone thickness. This definition applies not only to buccal/facial regions, but also to lingual/palatal peri-implant regions. Like the periodontal phenotype, the peri-implant phenotype is site-specific and may change over time in response to environmental factors (10). Peri-implant mucosa thickness is the horizontal dimension of peri-implant keratinized or non-keratinized soft tissue. Periimplant supracrestal tissue height is the vertical dimension of the soft tissue surrounding a dental implant from the mucosal margin to the crestal bone. Unlike keratinized mucosa width and mucosal thickness, this component of the peri-implant soft tissue phenotype courses circularly around an implant, including proximal regions. Peri-implant bone thickness is the horizontal dimension of the bone tissue supporting the osseotegrated implant. The optimal dimensions of all components of the phenotype to maintain peri-implant tissue health is a controversial issue. However, current studies show that keratinized mucosa, mucosal thickness and periimplant bone thickness are less than 2 mm; confirmed that marginal inflammation is greater in areas where the supracrestal tissue height is less than 3 mm (10). Biomarkers in peri-implant crevice fluid also provide promising results in terms of diagnostic

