The patients to be included in the research will be selected among 50 volunteer individuals aged between 18-65 who applied or were referred to Van Yüzüncü Yıl University Faculty of Dentistry Department of Periodontics with complaints of inflammation in the peri-implant area and were diagnosed with peri-implantitis disease. People who have systemic diseases, smokers, have used antibiotics or received any other medical treatment within 6 months, and are pregnant or breastfeeding will be excluded from the study. Additionally, individuals who

met the definition of peri-implant health and individuals who required surgical treatment of peri-implantitis were excluded from the study.

The peri-implant soft tissue phenotype of all participants who are detected to have periimplant disease and will be included in the study will be measured, necessary clinical and radiological examinations will be performed, necessary samples will be collected and conventional mechanical treatments will be applied. The data of all participants will be collected again in the 6th month following the treatment.

Patient Data Records, Peri-implant Disease Treatment

The details of the application and the research to be conducted will be explained to the patients who will participate in the study, and an informed consent form will be signed. Patients diagnosed with peri-implant disease will be asked for routine examinations before treatment, intraoral photographs will be taken, and clinical and radiological examinations will be performed in detail. Detailed anamnesis of patients who meet the selection criteria will be taken and clinical and radiological examinations will be performed. Patients with caries on their teeth will be directed to Restorative Dentistry Department and restorations of existing caries will be made at the relevant clinic. Before starting their treatment, patients who meet the selection criteria will be given detailed information about periodontal and peri-implant diseases, microbial dental plaque that causes these diseases, and methods of preventing microbial dental plaque. Individuals will be taught how to brush their teeth, how to use an interdental brush.

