Descriptive statistics for the features emphasized will be expressed as Median, Average, Standard Deviation, Minimum and Maximum value. In terms of these characteristics, two-factor and one of the factors repeated-measures analysis of variance will be used to compare group averages and periods (0th month and 6th month). To determine the relationship between variables, Pearson or Spearman correlation coefficients will be calculated separately in the groups. In the calculations, the statistical significance level will be taken as 5% and the SPSS statistical package program will be used for the calculations.

Figure- 1. Clinical Index Form

PLAQUE INDEX

REFERANCES

1 COSGAREA, Raluca; SCULEAN, Anton; SHIBLI, Jamil Avad And SALVI, Giovanni Edoardo. Prevalence Of Peri-İmplant Diseases – A Critical Review On The Current Evidence. Braz. Oral Res. [Online]. 2019, Vol.33, Suppl.1, E063. Epub Sep 30, 2019. ISSN 1807-3107.

5. Caton, J. G., Armitage, G., Berglundh, T., Chapple, I. L. C., Jepsen, S., Kornman, K. S., ... Tonetti, M. S. (2018). A new classification scheme for periodontal and peri-implant diseases and conditions - Introduction and key changes from the 1999 classification. Journal of Clinical Periodontology, 45, S1–S8. doi:10.1111/jcpe.12935

6. NOVAES JUNIOR, Arthur Belém et al. New strategies and developments for periimplant disease. **Braz. oral res.**, São Paulo , v. 33, supl. 1, e071, 2019 . access on 09 June 2020. Epub Sep 30, 2019.

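### The phenotype comparison is observational and unadjusted for baseline plaque, which the plan names as a cause and records; a plaque-adjusted result should be pre-specified beside it

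*Combined protocol and SAP*

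**What the plan says.** The Aim of Research has two parts: the effect of soft tissue phenotype on the degree of disease, and its contribution to the results of non-surgical treatment. The hypothesis is that "better clinical outcomes may be achieved in individuals with thicker soft tissue phenotype".

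Groups come from measurement. Under Patient Data Records, Peri-implant Disease Treatment, thickness below 1 mm by transgingival probing is thin, and above 1 mm "it will be classified as thick phenotype (15"). No randomisation, matching or stratification is described. Under Patient Selection and Study Protocol, participants are "selected among 50 volunteer individuals aged between 18-65", and for all of them "necessary samples will be collected and conventional mechanical treatments will be applied".

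On hygiene, the Scientific Basis section opens its list of contributors to tissue destruction with "Various risk factors (such as poor oral hygiene", and the patient-records section describes plaque as the cause of these diseases. Smokers and people with systemic disease are excluded; there is no restriction on hygiene or plaque. Everyone is taught brushing and interdental cleaning before treatment, and later "Oral hygiene instructions will be repeated when necessary". "Routine periodontal parameters such as plaque index (PI") are recorded before debridement, and all clinical parameters are measured again at month 6.

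The Statistical analysis section lists descriptive statistics, the analysis of variance ("two-factor and one of the factors repeated-measures analysis of variance will be used to compare group averages and periods (0th month and 6th month")) and correlations within groups. It names no covariate. It does not define the groups either; that they are phenotype groups follows from the aim, the hypothesis and the 1 mm classification.

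**The concern.** Groups formed by a patient characteristic can differ in anything associated with it. Here the plan identifies one such factor as causal, measures it before treatment, and leaves it out of the comparison. Two other factors on its own list are handled by exclusion, but plaque is not.

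If thin-tissue patients have more plaque, their gingival index, bleeding, pocket depth and biomarkers may be worse for that reason alone, and thickness would get the credit. If the imbalance runs the other way, a real thickness effect could be hidden. The planned correlations do not help, because they are calculated inside each group and do not adjust the difference between groups.

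**Working it through.** The plan gives no power, effect size, SD or group split, so it has no figure to reproduce. What follows is an illustration.

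**Inputs.** From the documents: 50 participants and a 5% significance level. Assumed: a two-sided test; two groups of 25; a plaque difference d of 0.3-0.8 within-group SD; a within-group plaque-outcome correlation r of 0.3-0.5; no true phenotype effect.

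**Single-visit comparison (baseline severity, for example).**
- Spurious group difference = d × r, in SD of the outcome.
- Non-centrality = d × r / √(1/25 + 1/25) = d × r / 0.283.
- False-positive rate = both tails of the non-central t with 48 degrees of freedom beyond the 5% critical value.

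| d | r | Spurious difference (SD) | Non-centrality | False-positive rate |
|---|---|---|---|---|
| 0.3 | 0.3 | 0.09 | 0.32 | 6.1% |
| 0.5 | 0.5 | 0.25 | 0.88 | 13.9% |
| 0.8 | 0.5 | 0.40 | 1.41 | 28.3% |

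With a 10/40 split the range is 5.7% to 19.8%. With d = 0 the rate is 5%.

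**Group-by-period test.** With two visits, this equals a two-sample t-test on the 0-6 month change. Let baseline plaque act on the outcome with slope b0 at month 0 and b6 at month 6. The spurious difference in change is then d × (b6 − b0).
- If b6 = b0, it is zero. Simulation with the same d and r and a stable plaque effect gave 4.8-5.3%.
- If baseline plaque does predict the change, the formula above applies with r read as the correlation between plaque and change. The documents give no value for that correlation.

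**Effect of adjustment on bias.** In simulations where plaque drives the analysed outcome (d from 0 to 1.0, r from 0.3 to 0.7, splits 25/25 and 15/35, 6,000 runs per cell), adding baseline plaque as a covariate gave false-positive rates of 4.6-5.5% and a mean bias near zero. This assumes that plaque is measured without error and acts linearly.

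**Effect of adjustment on precision.** The variance of the phenotype estimate changes by about (1 − r²) × [1 + (d²/48)/(2/25)].
- d = 0.8, r = 0.3: 0.91 × 1.167 = 1.06, a loss of about 6% in effective sample size.
- d = 0.3, r = 0.5: 0.75 × 1.023 = 0.77, a gain of about 30%.

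The sign depends on the assumptions, so no precision gain is claimed.

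**The case against.** The defence has real force on several points.

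- **The change test is protected against a constant plaque effect.** A reader might infer that the 6-28% applies to the planned test of treatment response. It does not, unless baseline plaque also predicts the change. The protection does not extend to the disease-severity part of the aim or to the ANOVA's group main effect.
- **Hygiene is not simply left alone.** All patients are taught plaque control before treatment, and repeating the instruction where needed may narrow plaque differences. It may also mean unequal co-treatment; no criterion or record is specified, so the documents do not settle which.
- **An imbalance would probably be seen.** Plaque index is a recorded parameter and, on a natural reading, gets the same descriptives and ANOVA as the others. A difference would then be visible, but still not adjusted for.
- **Plaque may lie on the causal path.** If thin tissue makes cleaning harder, adjusting even for baseline plaque removes part of the phenotype effect. The adjusted result therefore cannot stand alone.
- **Precision.** It is tempting to say that omitting plaque widens every interval. That holds when plaque is balanced between groups, but not throughout the range of imbalance assumed here.

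An analysis of month-6 values adjusted for the baseline outcome could be put in place of the change analysis. In non-randomised groups the two can disagree, and nothing in the documents requires that replacement.

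**Conclusion.** The point holds as a gap in the analysis plan. The comparison is observational, the plan names and measures a likely confounder, and the stated model omits it. A reader might go further and infer that plaque does differ by phenotype, or that the planned analysis is biased; the documents contain no data on plaque by phenotype and support neither.

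The 6-28% is conditional on the assumed plaque difference, correlation and 25/25 split, and it belongs to single-visit comparisons. The change test stays at about 5% when plaque acts equally at both visits.

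A separate matter limits what any plaque adjustment can do. The Scientific Basis section says that connective tissue grafts will be applied where thin tissue is found. Patient Selection and Study Protocol describes mechanical treatment for all and excludes those requiring surgical treatment of peri-implantitis. These passages must be reconciled, because a covariate for plaque cannot correct for a treatment given to one phenotype group only.

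**What to change.** In the Statistical analysis section:

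1. State that the groups are the phenotype groups, and keep the planned group-by-period ANOVA.
2. Tabulate baseline plaque index by phenotype group.
3. For every outcome other than plaque index, pre-specify a plaque-adjusted comparison beside the unadjusted one. At baseline, the model has phenotype and baseline plaque index. For treatment response, it is the 0-6 month comparison with baseline plaque index as covariate.
4. Do not adjust for month-6 plaque, which is measured after treatment and may be part of how phenotype acts.
5. Attribute a difference to phenotype only if the adjusted and unadjusted results agree. Otherwise report both and state that thin tissue may itself raise plaque.

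Reconcile the graft and mechanical-treatment passages separately.

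The cost is SAP wording and one degree of freedom in about 50 patients; plaque index is already collected. The downside is that the adjusted estimate may lose any part of the phenotype effect that works through plaque, which is why the unadjusted result stays beside it.
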